6.7. Dose Modification

The decision to proceed to the next dose level in both Part 1 (SAD) and Part 2 (MAD) will be made by the DEC, based on safety, tolerability, and preliminary PK data obtained from the prior dose level(s) as described in the Dose Escalation Committee Charter. Criteria for discontinuation of dose escalation also apply to discontinuation of dosing within the cohort in which a toxicity occurs.

6.8. Intervention after the End of the Study

Since only healthy participants are eligible for study participation, no additional treatment from Sponsor, including VH3739937, will be provided after the completion of the study.

7. DISCONTINUATION OF STUDY INTERVENTION AND PARTICIPANT DISCONTINUATION/WITHDRAWAL

7.1. Discontinuation of Study Intervention

A participant may be withdrawn from the study at any time:

- At his or her own request
- At the discretion of the Investigator in consultation with the Study Sponsor Medical Monitor for safety (including lab abnormalities or intercurrent illness), psychiatric, compliance, or administrative reasons.
- Emergence of any positive (abnormal) response confirmed by the investigator or a clinician (or qualified designee) administered CSSRS during the on-treatment phase (MAD only).
- \geq Grade 3 AE (or clinically significant laboratory abnormality) suspected to be related to VH3739937
- A SAE, regardless of its severity, that is considered be clinically significant and reasonably attributable to dosing with VH3739937, in the opinion of the Investigator.
- A grade ≥ 2 rash with concurrent fever with or without concurrent elevations in liver biochemistry reasonably attributable to dosing with VH3739937, in the opinion of the Investigator.
- Termination of the study by the Sponsor. Safety data will be reviewed by the Sponsor in-stream by single case and collectively. If a safety concerns arises, a decision about continuation of the study will be made.
- Loss of ability to freely provide consent due to incarceration or involuntary treatment of either a psychiatric or physical (eg, infectious disease) illness
- Unblinding of unauthorized Site Staff, including the PI, for any reason

- Repeat non-adherence by the participant with the requirements of the protocol or treatment (as determined by Investigator in consultation with the Study Sponsor Medical Monitor)
- Pregnancy (Section 10.4.3)
- PK stopping criteria is met (Section 7.1.4)
- Clinical criteria for stopping study is met (Section 7.1.5)

If the participant withdraws consent for disclosure of future information, the Sponsor may retain and continue to use any data collected before such a withdrawal of consent. If a participant withdraws from the study, he/she may request destruction of any samples taken and not tested, and the investigator must document this in the site study records.

If a participant chooses to withdraw from the study, he/she will complete a follow-up visit as per [SoA](#).

7.1.1. Liver Chemistry Stopping Criteria

[figure not shown]
Liver chemistry stopping and increased monitoring criteria have been designed to assure participant safety and evaluate liver event etiology.

Discontinuation of study intervention for abnormal liver tests is required when:

- A participant meets one of the conditions outlined in [Figure 5](#) below.
- When in the presence of abnormal liver chemistries not meeting protocol-specified stopping rules, the investigator believes study intervention discontinuation is in the best interest of the participant.

Study intervention will be discontinued **for a participant** if liver chemistry stopping criteria are met:

Figure 5 Phase I Liver Chemistry Stopping Criteria – Liver Stopping Event Algorithm

Abbreviations: ALT = alanine transaminase; INR = international normalized ratio; SAE = serious adverse event; ULN = upper limit of normal.

Details of Liver Safety Required Actions and Follow-Up Assessments can be found in [Appendix 5](#).

7.1.1.1. Study Intervention Restart or Rechallenge after liver stopping criteria met

Study intervention restart or rechallenge after liver chemistry stopping criteria are met by any participant in this study is not allowed.

7.1.2. QTc Stopping Criteria

The QTcF *must* be used for *each individual participant* to determine eligibility for and discontinuation from the study. This formula may not be changed or substituted once the participant has been enrolled.

The QTcF stopping criteria is based on averaged QTcF values of triplicate electrocardiograms obtained over a brief (e.g., 5-10 minute) recording period.

A participant that meets either bulleted criterion based on the average of triplicate ECG readings will be withdrawn from study treatment.

- QTcF >500 msec,
- Change from baseline: QTcF >60 msec

See the [SoA](#) for data to be collected at the time of intervention discontinuation and follow-up and for any further evaluations that need to be completed.

7.1.3. Temporary Discontinuation

Temporary discontinuation in this study is not allowed.

7.1.4. PK Stopping Criteria for SAD and MAD

In the SAD, the PK stopping criteria are based on mitigating any potential for Cmax mediated effects on ECG parameters. There were no ECG or other CV effects in a good laboratory practice (GLP) single-dose CV study in telemeterized dogs (Cmax = 9.82 $\mu\text{g}/\text{mL}$) and a 1-month GLP study in dogs (Cmax = 39.8). The stopping criteria is conservatively based on lower Cmax in the CV study in telemeterized dogs where there were no CV effects (9.82 $\mu\text{g}/\text{mL}$), equivalent to 21 $\mu\text{g}/\text{mL}$, when adjusted for protein binding. Protein binding is higher in human (93%) compared to dog (85%). If safety or PK stopping criteria are not met for the current/prior doses, dose escalation in Part 1 (SAD) will be stopped in the event that the Bayesian predicted probability is $>50\%$ that any participant's Cmax for the next subsequent dose will exceed 21 $\mu\text{g}/\text{mL}$ (the SAD PK stopping criteria).

In the MAD, the PK stopping criteria are based on AUC exposures where VH3739937-related microscopic findings were observed in the stomach of rats and dogs in the GLP 1-month oral toxicity studies. Corresponding Cmax exposures are expected to be below 21 $\mu\text{g}/\text{mL}$. A NOAEL was identified for microscopic findings in the stomach of rats at 10 mg/kg/day and a LOAEL in rats was identified at 40 mg/kg/day. A NOAEL for microscopic findings in the stomach of dogs was not identified and the LOAEL in dogs was 3 mg/kg/day. At the LOAEL in rats and dogs, VH3739937 was well tolerated and resulted in minimal, reversible single cell necrosis of parietal cells and chief cells. Exposure at the LOAEL in rats was AUC = 96.2 $\mu\text{g}^*\text{h}/\text{mL}$ and in the dog was AUC = 51.9 $\mu\text{g}^*\text{h}/\text{mL}$. The LOAEL in rats was chosen as the PK stopping criteria, and exposure is approximately 4-fold higher than the AUC in rats at the NOAEL dose of 10 mg/kg/day. The selection of the higher LOAEL AUC from the two preclinical species arises from the need to achieve sufficiently high exposures for cardiodynamic assessment of the TQT prolongation risk and mitigate the need for a TQT study. In the absence of data on the effect of intrinsic and extrinsic factors on the PK of VH3739937, and at the time of study initiation, the typical targeted doses were ~ 4 x the minimal predicted efficacious dose.

Dose escalation in Part 2 (MAD) will be stopped in the event that safety or PK stopping criteria are not met, but if the Bayesian predicted probability is $>50\%$ that any participant's AUC(0- τ) on Day 14 in the subsequent Cohort 3 and 4, or on Day 18 in Cohort 5, or on or prior to Day 21 in Cohort 6 will exceed the MAD PK stopping criteria. In the event this occurs, the dose for the next cohort may be reduced such that the Bayesian predicted probability that any participant's AUC(0- τ) and the Cmax on Day 14 in the subsequent dose will exceed the MAD PK stopping criteria is $\leq 50\%$.

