The duration of dosing in Cohort 5 is to support up to 18-day dosing as an oral lead for the future SAD and MAD studies of the long acting formulation of VH3739937. This duration is to potentially allow the identification of any early drug hypersensitivity reactions (HSR) which may occur before the administration of the long acting formulation. In each escalating dose cohort, 7 participants will be randomized to receive VH3739937 and 3 participants will be randomized to receive placebo (PBO). Dose escalation in Part 2 will be determined by the VH/GSK study team and the PI based on the double-blind (sponsor-unblinded) safety and PK data (minimally up to 15 days following the last dose) from the previous dosing Cohort(s). Specifically, safety and PK data through Day 29 in Cohorts 3 and 4, and through Day 33 in Cohort 5 from a minimum of 5 participants receiving active drug will be required for dose escalation.

Part 2 of the study was initiated once the single dose safety and preliminary PK data was evaluated in the SAD and the maximum exposure for the first MAD dose in Cohort 3 was covered by the SAD certain dose level. The potential minimally effective daily dose for VH3739937 with the suspension formulation was determined by the modeling and simulation utilising data for all doses in Part 1, as 25 mg, and is anticipated to be that which is predicted to provide a steady state $C\tau \geq 0.258 \mu\text{g/mL}$ in 95% of participants.. More detailed information may be found in the IB Supplement [GlaxoSmithKline Document Number 2021 [RPS_CLIN_004025](#)].

Dose escalation in the MAD will not exceed 2-fold between cohorts 3 to 5 and will be driven by safety and PK stopping criteria (see Section [7.1.4](#)). The 500 mg dose included in the MAD Cohort 6 was determined following modelling and simulation of PK data acquired in the SAD treatment periods through to 640 mg and MAD Cohort 3. In addition, a dose will not be assessed in the MAD until the anticipated steady-state exposure (C_{\max} and $AUC(0-\tau)$ on Day 14 for Cohorts 3 and 4, on Day 18 for Cohort 5 and at Day 14 following the third QW dose in Cohort 6) for that dose have been evaluated and shown not to have met safety stopping criteria in the SAD portion of the study (Part 1).

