Vital signs		X	X	X (Days 2, 4, and 6)	X	X (Days 10, 12 and 14)	X	X		X		X		Vital signs to be performed pre-dose. Temperature will be monitored every day during study participation. For further detail, see Section 8.1.2
12-lead safety ECGs		X	X	X	X	X	X	X	X	X	X	X		ECG should be performed pre-dose on dosing days. ECG timepoints may be reduced in subsequent dosing groups. For further detail, see Section 8.1.4
Testing for SARS CoV-2	X			X (Day 7)		X (Day 14)						X		An additional SARS-CoV-2 test will be performed approximately one week prior to admission to the unit. Weekly SARS-CoV-2 testing is required while in the unit (Days 7, 14) and on discharge (Day 20). An approved molecular

Procedure	Pre-Treatment Days		Week 1		Week 2		Week 3		In House Post Treatment Days					Notes
	Treatment Days		Treatment Days		Treatment Days									
	-2	-1	1	2, 3, 4, 5, 6, 7	8	9, 10, 11, 12, 13, 14	15	16 24h	17 48h	18 72h	19 96h	20 120h		
														Hours (h) relate to PK sampling post last dose
Drug/alcohol/nicotine screen	X													test (PCR) will be used. For further detail see Appendix 7 and Section 8.1.3
Haematology/Chemistry/Urine tests		X	X	X (Days 2, 4 and 6)	X	X (Days 9, 11 and 13)	X		X		X	X		For further detail, see Appendix 2
Pregnancy Test	X													Female participants only. For further detail see Appendix 2
VH3739937 Dose Administration			X		X		X							Weekly oral dose on Days 1, 8 and 15. Randomization to occur on Day 1 prior to dosing. For meal instructions prior to dose, see Section 5.3.1
Meals	Per site usual practice													
Plasma PK Sampling			X	X	X	X	X	X	X	X	X	X		2mL of blood will be collected at pre-dose (within 15 mins prior to dosing) and 1, 2, 3, 4, 5, 6, 7, 8, 9, 10, 12, and 16 h on Days 1, 8 and Day 15. The 24 h post day 1 dose collection on Days 2, 9 and 15 will be taken at post-dose collection timepoint. At all other timepoints on non-dosing days (Days 3, 4, 5, 6, 7, 10, 11, 12, 13, 14, 16, 17, 18, 19, 20), samples will be drawn at the post-dose

Procedure	Pre-Treatment Days		Week 1		Week 2		Week 3		In House Post Treatment Days					Notes		
	Treatment Days		Treatment Days		Treatment Days											
	-2	-1	1	2, 3, 4, 5, 6, 7	8	9, 10, 11, 12, 13, 14	15	16 24h	17 48h	18 72h	19 96h	20 120h				
Urine PK			X	X (Day 2, end of 24hr collection from Day 1)	X	X (Day 9, end of 24hr collection from Day 8)	X	X (Day 16, end of 24hr collection from Day 15)						Hours (h) relate to PK sampling post last dose		

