The duration of dosing in Cohort 5 is to support up to 18-day dosing as an oral lead for the future SAD and MAD studies of the long acting formulation of VH3739937. This duration is to allow the identification of any early drug hypersensitivity reactions (HSR) which may occur before the administration of the long acting formulation. In each escalating dose cohort, 7 participants will be randomized to receive VH3739937 and 3 participants will be randomized to receive PBO. Details of the starting dose and dose escalations in Part 2 (MAD) are provided in Section 4.3.

Part 2 of the study was initiated once the single dose safety and preliminary PK data were evaluated in the SAD and the maximum exposure for the first MAD dose was covered by the SAD certain dose level. The potential minimally effective daily oral dose for VH3739937 with the suspension formulation was determined by the modeling and simulation utilising data for all doses in Part 1, as 25 mg, and is anticipated to be that which is predicted to provide a steady state $C\tau \geq 0.258 \mu\text{g/mL}$ in 95% of participants. More detailed information may be found in the IB Supplement [GlaxoSmithKline Document Number 2021 [RPS_CLIN_004025](#)].

Dose escalation in the MAD will not exceed 2-fold between cohorts 3 to 5 and will be driven by safety and PK stopping criteria (see Section 7.1.4). The 500 mg dose included in the MAD Cohort 6 was determined following modeling and simulation of PK data acquired in SAD treatment periods through to 640mg and in MAD Cohort 3. In addition, a dose will not be assessed in the MAD until the anticipated steady-state exposure (C_{\max} and $AUC(0-\tau)$ on Day 14) for that dose have been evaluated and shown not to have met safety stopping criteria in the SAD portion of the study (Part 1).

For Part 2 MAD Cohorts 3, 4 and 5, 24-hour continuous Holter/ECG recordings will be collected, on the day before the first dose (Day -1), Day 1, and Day 14 for extraction of ECGs paired with PK sampling. In addition, 12-Lead ECGs will be collected for Part 2 at timepoints indicated in the SoA.

Participants in Part 2 will have a screening visit within 28 days prior to first dose and a follow-up visit approximately 28 days after the last dose. Flexibility of visit scheduling may be required if a pandemic situation applies (see [Appendix 7](#)). Otherwise, study

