Treatment Assignment	
Part 1 (SAD):
 
 Participants in either Cohort 1 or Cohort 2 will be assigned to 1 of the 3 treatment sequences in a cross-over, and each participant will receive placebo once. 
  
 Cohort 1	Period 1	Period 2	Period 3	
   
 Sequence 1	Placebo	Dose 3	Dose 5	
 
 Sequence 2	Dose 1	Placebo	Dose 5	
 
 Sequence 3	Dose 1	Dose 3	Placebo	
  
 
  
 Cohort 2	Period 1	Period 2	Period 3	
   
 Sequence 1	Placebo	Dose 4	Dose 6	
 
 Sequence 2	Dose 2	Placebo	Dose 6	
 
 Sequence 3	Dose 2	Dose 4	Placebo	
  
 
 When the 800 mg dose is evaluated, 9 new participants, who were not previously exposed to any dose of VH3739937 will be enrolled in the study. Six participants randomized to receive VH3739937 and 3 participants will be randomized to receive placebo. 
Part 2 (MAD):
 
 In Cohorts 3 to 5, 10 participants per cohort (active/PBO=7/3) will receive a once-daily dose of VH3739937 or PBO for 14 days (Cohort 3 and 4) or 18 days (Cohort 5) In Cohort 6, 10 participants (active/PBO=7/3) will receive a once-weekly dose of 500 mg VH3739937 or PBO over the course of 14 days (Doses on Day 1, 8, and 15) 	Cohort 1	Period 1	Period 2	Period 3	Sequence 1	Placebo	Dose 3	Dose 5	Sequence 2	Dose 1	Placebo	Dose 5	Sequence 3	Dose 1	Dose 3	Placebo	Cohort 2	Period 1	Period 2	Period 3	Sequence 1	Placebo	Dose 4	Dose 6	Sequence 2	Dose 2	Placebo	Dose 6	Sequence 3	Dose 2	Dose 4	Placebo
Cohort 1	Period 1	Period 2	Period 3																														
Sequence 1	Placebo	Dose 3	Dose 5																														
Sequence 2	Dose 1	Placebo	Dose 5																														
Sequence 3	Dose 1	Dose 3	Placebo																														
Cohort 2	Period 1	Period 2	Period 3																														
Sequence 1	Placebo	Dose 4	Dose 6																														
Sequence 2	Dose 2	Placebo	Dose 6																														
Sequence 3	Dose 2	Dose 4	Placebo																														

Overview of Study Design and Key Features	

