8.1.5.1.2. Accumulation Ratio

Part 1

Predidicted daily dose accumulation from single dose data (Part 1) for AUC will be as follows:

$$Rp(AUC) = \frac{AUC(0 - \infty)}{AUC(0 - 24)}$$

Point estimates of the mean ratio and associated 90% confidence intervals will be displayed by treatment.

Part 2

Accumulation will also be evaluated for each treatment by determining the ratio of Day 14 (Part 2 cohort 3 and 4) or Day 18 (Part 2 cohort 5) to Day 1 AUC(0- τ) (R(AUC(0- τ)), Cmax (R(Cmax)), and C τ (R(C τ)). Day 1 C τ will be defined as the 24-hr post day 1 dosing concentration (C24 for Day 1). For part 2 cohort 3,4, and 5 the dosing interval is 24-hrs. Therefore, $\tau=24$ hrs.

For Cohort 6 accumulation will be evaluated by determining the ratio of third dose (occurring on Day 15) to first dose (Day 1) for AUC(0- τ) (R(AUC(0- τ)), Cmax

(R(Cmax)), and C τ (R(C τ)). For part 2 cohort 6 the dosing interval is 7 days (168 hrs). Therefore, $\tau=168$ hrs. In Cohort 6, since sampling at 168 hrs post 3rd dose was not collected, it will be predicted using linear model based on the other collected timepoints post dose.

Point estimates of the mean ratios and associated 90% confidence intervals will be displayed by treatment.

Endpoint / Variables

 • Rp(AUC) for Part 1 Where $Rp(AUC) = \frac{AUC(0 - \infty)}{AUC(0 - 24)}$ • R(AUC(0-τ)), R(Cmax), R(Cτ) on Days 1 and 14 for Part 2 Cohort 3 and 4 where, $\tau=24$ hrs • R(AUC(0-τ)), R(Cmax), R(Cτ) on Days 1 and 18 for Part 2 Cohort 5 where, $\tau=24$ hrs • R(AUC(0-τ)), R(Cmax), R(Cτ) on Days 1 and 15 for Part 2 Cohort 6 where, $\tau=168$ hrs 
Where
 $R(Parameter) = \frac{(Parameter\ Value\ on\ Day\ XX)}{(Parameter\ Value\ on\ Day\ 1)}$
Model Specification

 • In Part 1 the mean of the raw mean of the ratio of AUC(0-inf) to AUC(0-24) will be reported. There is no formal modeling. • In the model for Part 2 Cohort 3,4,5,6 the ratio of the specific parameter will be the dependent variable, day will be included as a fixed effect categorical variable with the reference as Day 1, and participant will be included as a random effect.
Model Checking & Diagnostics

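### Protocol 7.1.4 and the Table 9 title test Cohort 6's weekly AUC(0-τ) against a daily limit of 96.2 µg·h/mL; the maximum 24-hour AUC was meant, and the wording should say so

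*Protocol*

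**What the plan says.** **The rule.** Section 7.1.4 sets the MAD limit at the rat LOAEL exposure, 96.2 µg·h/mL, from dosing at 40 mg/kg/day. Escalation stops if the predicted probability exceeds 50% that any participant's AUC(0-τ) "on or prior to Day 21 in Cohort 6 will exceed the MAD PK stopping criteria". The fallback begins "In the event this occurs, the dose for the next cohort may be reduced such that the Bayesian predicted probability" and covers AUC(0-τ) together with "the Cmax on Day 14 in the subsequent dose will exceed the MAD PK stopping criteria", which must be at most 50% probable.

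**The interval.** AUC(0-τ) is defined under the objectives table (Protocol Section 3) as running to the end of the dosing interval. SAP 8.1.5.1.2 states: "For part 2 cohort 6 the dosing interval is 7 days (168 hrs".

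**The metric used elsewhere.** The Table 9 title repeats AUC(0-τ) against 96.2 for 500 mg weekly and reports 0. The paragraph above it refers to AUC(0-24). Footnote f to Table 11 says the maximum 24-hour AUC was taken so as to be comparable with a limit it describes as daily. Section 9.5 uses a maximum daily AUC of 31.2.

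**The days.** The schedule for Cohort 6 is "Weekly oral dose on Days 1, 8 and 15", and SAP 2.3 agrees: "over the course of 14 days (Doses on Day 1, 8, and 15". Yet Section 4.1 dates MAD exposure without distinguishing cohorts, "on Day 14) for that dose have been evaluated and shown not to have met safety stopping criteria in the SAD portion", and the synopsis has "at Day 14 following the third QW dose in Cohort 6".

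**The concern.** A weekly AUC accumulates seven days of exposure, whereas the limit is one day's. A dose-stopping rule in healthy volunteers should be executable as printed, and Section 1.2 allows no waivers. Applied as written, this rule would stop 500 mg weekly, which Section 4.1 gives as the predicted efficacious weekly dose, while Table 9 reports zero risk under the same AUC(0-τ) label. The Day 14 references also fail for Cohort 6, because Day 14 falls before the third dose.

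Two nearby items support the same dose decisions and need correction. Table 8 is labelled as the probability for any MAD participant, but its values look like one participant's. In 9.5, N counts the iterations that exceed the threshold, yet the probability is printed as 1 − N/10,000, and θ2 is multiplied by 800 although the model is in log-dose.

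**Working it through.** **Inputs.** Limit 96.2 (7.1.4). Table 11 medians for 500 mg weekly: Cmax 1.5, Cτ 0.429, 24-hour AUC 31.3. Half-life about 90 h and 7 active participants per cohort (4.1). Median 24-hour AUC at 100 mg daily 39.8 (Table 11).

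**Assumptions.** Exposure is lognormal with σ = √ln(1+CV²), that is 0.246, 0.340 and 0.472 at CV 25, 35 and 50%. Then p = 1 − Φ((ln 96.2 − μ)/σ) and any-of-7 = 1 − (1−p)^7. The stated AUC is taken either as the median (μ = ln AUC) or as the mean (μ = ln AUC − σ²/2).

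**1. Reproducing Table 9.** With 31.3 as median and CV 25%, z = ln(96.2/31.3)/0.246 = 4.56, p = 0.0000026 and any-of-7 = 0.00002 (0.00001 with 31.3 as mean). This prints as 0, so Table 9 was computed on the 24-hour AUC.

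**2. AUC(0-168) at 500 mg weekly.** The documents give no value, so I derived a range.
- (1.5 − 0.429)/k with k = ln 2/90 = 0.00770: 139.
- The same with k = ln(1.5/0.429)/168 = 0.00745: 144.
- Seven daily AUCs, 31.3 × Σ exp(−24ki) for i = 0 to 6: 135 and 136.

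**3. The rule read literally.** Most favourable case (135 as mean, CV 50%): p = 0.68, any-of-7 = 0.9997. Least favourable (144 as median, CV 25%): p = 0.95, any-of-7 essentially 1. Even a floor that holds concentration at Cτ after the first day, 31.3 + 144 × 0.429 = 93.1, gives any-of-7 of 0.96–0.99. All are far above 50%.

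**4. Table 8, 100 mg daily (AUC 39.8).** Ranges span the mean and median readings.

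| CV | Printed | One participant | Any of 7 |
|---|---|---|---|
| 25% | <0.001 | 0.0001–0.0002 | 0.0007–0.0012 |
| 35% | 0.003 | 0.003–0.005 | 0.020–0.033 |
| 50% | 0.028 | 0.018–0.031 | 0.12–0.20 |

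The printed values fit one participant.

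**5. The 9.5 formula at 800 mg.** The predicted median Cmax is 1.60 (4.3.3) and the threshold is 21. I take CVw = CVb = 50%, slope 1, the Table 7 layout, six predicted subjects and variances treated as known. Over 1000 simulated trials the correct form, N/10,000 with log(800) = 6.68, averages 0.001 with a maximum of 0.015. This agrees with the protocol's statement that every trial fell below 40%. With log(800) but 1 − N/10,000 the value would be about 0.999, which does not agree.

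**6. Cross-check on Table 15.** I simulated 7 participants each at 25 and 50 mg and predicted any of 7 at 100 mg. The share of trials below the 40% threshold, from CV 25% to CV 50%:
- printed: 0.995 falling to 0.791;
- exceedance form, N: 0.99 falling to about 0.60;
- complement form, 1 − N: 0.001 rising to about 0.18.

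The design behind Table 15 is not fully specified, so only the direction is comparable. It matches the exceedance form.

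**The case against.** The best reply is that the intent is plain. Three places in the protocol use the 24-hour AUC, and Table 9's 0 can come from nothing else. Section 9.5 describes the probability as one aid to dose selection, the fallback is permissive, and the Dose Escalation Charter, which was not available here, may state the metric correctly. The intent is indeed clear, so this is a wording fault and not a dosing fault. But 7.1.4 is the stated stopping rule, its stop is not conditional, and it names AUC(0-τ).

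On Table 8, neither the mean nor the median reading reproduces both the CV 35% and the CV 50% cells. The input exposure is not printed there, and the label could mean any given participant. Table 15 already shows the decision-level risk at high CV. That is why the relabelling is offered with moderate confidence only.

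Four stronger inferences are tempting, and the documents do not support them.
- **The 800 mg result could be an artefact.** With both misprints in the code every draw would exceed log(21), the printed probability would be 0, and every trial would again fall below 40%. But the same code applied to Table 15 would give essentially 1 in every cell, and the printed values are graded.
- **The protocol calls for a lower weekly dose.** That follows only from the unintended metric.
- **The Day 21 cut-off proves the error**, because 168 h after a Day 15 dose ends on Day 22. The interval covers study Days 15 to 21, so the cut-off is compatible with either metric.
- **The weekly simulation is wrong**, because its CV list reads 25, 35, 5. If 5 means 50, about 30–58 of 1000 trials should show an exceedance, where none is reported. A lost digit is possible, so this is a query only.

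**Conclusion.** The metric for Cohort 6 is wrong as written in 7.1.4 and in the Table 9 title. Taken literally, any-of-7 exceedance is above 0.999 and 500 mg weekly is stopped. On the intended 24-hour metric it is about 0.00002 at CV 25% and no planned dose changes. The size rests on lognormal exposure and on an AUC(0-168) derived from Table 11; the conclusion survives the floor of 93.1.

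A reader might infer that volunteers could be over-exposed. The opposite is true: the printed rule is too strict, and it adds no risk.

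The secondary points are smaller. Any-of-7 values for 100 mg daily are less favourable than Table 8 suggests at CV 35–50%, but they stay below 50%. The 9.5 formula is most likely a misprint only, and the rerun supports the 800 mg conclusion. Confidence is high for the metric and the formula, and moderate for Table 8. This should be fixed, but it does not threaten the trial.

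**What to change.** - **Main change.** In 7.1.4 and the Table 9 title, state that for Cohort 6 the quantity compared with 96.2 µg·h/mL is the maximum AUC(0-24) after the Day 15 dose. Correct the Day 14 references for Cohort 6 in the 7.1.4 dose-reduction sentence, in 4.1 and in the synopsis.
- **Table 8.** Relabel it as per participant, or print any-of-7 values (100 mg daily: about 0.001, 0.02–0.03 and 0.12–0.20 at CV 25, 35 and 50%).
- **Section 9.5.** Print N/10,000 and θ2 × log(800), with a brief confirmation from the code. Clarify the weekly CV list; rerun that simulation only if the last value was meant to be 50.

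The cost is a few sentences, one or two table labels, a short code check and possibly one rerun. No dose, sample size or assessment changes.
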